## 4 STUDY DESIGN AND ENDPOINTS

### 4.1 DESCRIPTION OF THE STUDY DESIGN

The study has a 2x2 crossover design. Participants will take either the placebo or resveratrol for 90 days followed by a 30 day washout period and the placebo or resveratrol for the last 90 days. 30 day washout period was chosen in order to eliminate any carry over from resveratrol as it is recommended to avoid resveratrol 2 weeks prior to surgery suggesting that carry over could potentially be as long as 2 weeks (<http://www.webmd.com/vitamins-supplements/ingredientmono-307-resveratrol.aspx?activeingredientid=307>; <http://ww5.komen.org/BreastCancer/Resveratrol.html>). Participants will be mailed a 30 or 90 day (for international participants) supply of placebo or resveratrol which they will receive 5 days before the end of each 30 day period (not applicable for international participants). Participants will keep daily pain log of pain and activity levels during the entire 210 day study period. We recognize that this is a long period of time however this population is highly motivated because 1) their pain is not systematically treated, 2) currently available over the counter NSAIDs, frequently used to control pain, cause gastrointestinal issues when used for prolonged periods and 3) participants reached through Little People of America and the PSACH facebook page are actively seeking solutions to control pain. This is being co-ordinated by a single center and will enroll 30 PSACH individuals. Because this is a rare condition, participants from 18 years - to 70 years will be enrolled.

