### 5.3 STRATEGIES FOR RECRUITMENT AND RETENTION

Recruitment will be conducted at Little People of America convention (n=300 PSACH members) and the PSACH blog (Facebook page: "Pseudoachondroplasia Dwarfish – and growing!!!" Closed group with 211 members). We will be recruiting International participants that contact us with interest in the study or that international colleagues refer to us. This recruitment strategy reaches out to the most active population in order to recruit motivated participants

that will complete the 7 month study. Monthly calls to participants to assess compliance and record keeping as well as any adverse events will be done to increase retention.

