7.2.4 SPECIMEN SHIPMENT

NA

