7.3.2 ENROLLMENT/BASELINE

**Baseline Phone call (Visit 1, Day 0)**

- Patient will be contacted after receipt of initial study package via postal mail (including medications and information for blood draw to assess kidney function, liver function and blood cell count). The complete metabolic panel includes analysis of renal function [blood urea nitrogen (BUN), creatinine], liver function [total bilirubin, alanine aminotransferase (ALT), alkaline phosphatase (ALP), and aspartate aminotransferase (AST)], glucose, electrolytes [calcium, sodium, potassium, carbon dioxide (bicarbonate), chloride], protein [albumin, total protein]. The complete blood count (CBC) includes analysis of red blood count, hemoglobin, hematocrit, white blood cell count, platelet count. Platelet count below 50,000 per  $\mu\text{l}$  in CBC which indicates increased bleeding risk will result in exclusion.
- For Participants in the United States they will be asked to complete blood draw to the closest LabCorp or from their local facility at our cost. For the International participants blood need to be draw from a local facility an mailed to us for analysis at the local labcorp lab.

- Query participants about any changes in inclusion/exclusion criteria.
- Patients will be asked to start taking study medication on the next day.
- Administer HRQoL instrument.

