#### **Follow-up Visit (Visit 4, Day 90 +/- 5 working days)**

- Inform patient that they are supposed to not take any study medication for the next 30 days but should continue their pain logs.
- Record adverse events as reported by participant to study co-ordinator. Study coordinator will ask about gastrointestinal health, any bleeding events and unusual bruising. PI will follow up with participant to assess the adverse events and determine whether to terminate participation.
- Record participant's adherence to treatment protocol.
- Inquire about any medication and health condition changes.
- Administer HRQoL instrument.
- Request participant to mail back or email their pain log and mail back any unused medication or email a photo of the empty bottle. The data from the pain logs will be compiled and analyzed at the start and end of each two treatment periods (on days 0, 90, 120, and 210).
- Ask participants about which medication, resveratrol or placebo, they think they were taking during the last 90 day period (evaluation of the success of blinding).
- Female participants in the United States will be asked to take a urine pregnancy test at local labcorp or local lab. Email a photo of self administered pregnancy test supplied by us for female international participants within 30 days prior to next medication mail out.
- Participants will be asked to complete blood draw to the closest LabCorp or from their local facility at our cost. For the International participants complete blood draw to the closest local facility blood and mailed to us for analysis at local Labcorp lab.
- The complete metabolic panel includes analysis of renal function [blood urea nitrogen (BUN), creatinine], liver function [total bilirubin, alanine aminotransferase (ALT), alkaline phosphatase (ALP), and aspartate aminotransferase (AST)], glucose, electrolytes [calcium, sodium, potassium, carbon dioxide (bicarbonate), chloride], protein [albumin, total protein]. The complete blood count (CBC) includes analysis of red blood count, hemoglobin, hematocrit, white blood cell count, platelet count. Platelet count below 50,000 per  $\mu$ l in CBC which indicates increased bleeding risk will result in removal from the study.

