7.3.4 FINAL STUDY VISIT

**Final Study Visit (Visit 8, Day 210 +/- 5 working days)**

- Inform patient that they have completed the study.
- Record adverse events as reported by participant to study co-ordinator. Study coordinator will ask about gastrointestinal health, any bleeding events and unusual bruising. PI will follow up with participant to assess the adverse events and determine whether to terminate participation.
- Record participant’s adherence to treatment protocol.
- Inquire about any medication and health condition changes.
- Participants will be asked to complete blood draw from their local facility at our cost to assess kidney function, liver function and blood cell count. The complete metabolic panel includes analysis of renal function [blood urea nitrogen (BUN), creatinine], liver function [total bilirubin, alanine aminotransferase (ALT), alkaline phosphatase (ALP), and aspartate aminotransferase (AST)], glucose, electrolytes [calcium, sodium, potassium, carbon dioxide (bicarbonate), chloride], protein [albumin, total protein]. The complete blood count (CBC) includes analysis of red blood count, hemoglobin, hematocrit, white blood cell count, platelet count. Platelet count below 50,000 per µl in CBC which indicates increased bleeding risk will result in removal from the study.
- Administer HRQoL instrument.
- Request participant to mail back or email their pain log and mail back any unused medication or email a photo of the empty bottle. The data from the pain logs will be compiled and analyzed at the start and end of the two treatment periods (on days 0, 90, 120, and 210).
- Ask participants about which medication, resveratrol or placebo, they think they were taking during the last 90 day period (evaluation of the success of blinding).

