### 8.5 STUDY HALTING RULES

Administration of study agent will be halted study-wide when any of the following occur and are reported to the DSMB:

- three grade 3 AEs
- three grade 1 or grade 2 AEs of the same type
- three grade 1 or grade 2 AEs related to liver function
- one grade 4 or 5 AE

The research coordinator will notify the principal investigators and co-investigator immediately when the the study stopping criteria are met and enrollment screens will stop accepting new study participants. The principal investigator will inform the Data and Safety Monitoring Board (DSMB) members within 24 hours of this occurrence and will provide the DSMB with AE listing reports. The DSMB will convene an ad hoc meeting by teleconference or in writing as soon as possible. The DSMB will provide recommendations for proceeding with the study to the principal investigator. The principal investigator will inform the FDA of the temporary halt and the disposition of the study.

An individual participant will be asked to discontinue study medication if any of the following occur:

- one grade 3, 4, or 5 AE
- three grade 2 AEs
- five grade 1 AEs

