##### 13.4.1 RESEARCH USE OF STORED HUMAN SAMPLES, SPECIMENS OR DATA

No human samples or specimens will be collected during this study

Data collected will be analyzed to determine if resveratrol has any benefit for pain in PSACH.

Storage: Access to stored data will be limited using password electronic protection and locked file cabinets. Data will be stored using codes assigned by the investigators. Data will be kept in password-protected computers. Only investigators will have access to the samples and data.

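### International participants' blood is mailed to the study for CBC and chemistry at baseline and Day 90 with no handling rules, yet the platelet criteria and laboratory-graded stopping rules act on the results

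*Combined protocol and SAP*

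**What the plan says.** International enrolment is planned: section 5.3 states "We will be recruiting International participants that contact us with interest in the study". No number or share is given. The total in section 4.1 is that the study "will enroll 30 PSACH individuals" (section 10.6.1 gives one hundred; that conflict is separate).

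The laboratory route depends on where the participant lives and on the visit:

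- **Baseline, section 7.3.2.** US participants go to the nearest LabCorp or a local facility. For the others: "For the International participants blood need to be draw from a local facility an mailed to us for analysis at the local labcorp lab".
- **Day 90, section 7.3.3.** The same split: "For the International participants complete blood draw to the closest local facility blood and mailed to us for analysis at local Labcorp lab".
- **Day 210, section 7.3.4.** All participants are to "complete blood draw from their local facility at our cost to assess kidney function" and the other panel results. Nothing is said about mailing or about where the sample is analysed.

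The panel comprises a CBC with platelet count and a metabolic panel with potassium, creatinine, bilirubin and liver enzymes.

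The sections that should govern this are empty. Sections 7.2.1 to 7.2.4, the last headed "SPECIMEN SHIPMENT", all read NA. Section 13.4.1 adds: "No human samples or specimens will be collected during this study".

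**The concern.** A cell count has to be made on blood whose cells are still in it, so separating the sample before posting is no way round the problem for platelets. The plan puts a shipping step of unknown length and conditions between draw and measurement, for one group of participants only. It has no rule for rejecting or repeating a doubtful sample.

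Firm consequences hang on the results. A platelet count under 50,000 per microlitre excludes at baseline (5.2, item 10; 7.1.1; 7.3.2) and removes at Day 90 (7.3.3). Section 8.2.1 grades platelets, haemoglobin, potassium, creatinine and liver tests. Under section 8.5 a single grade 3 event stops the participant's study medication. The study-wide halt is reached by "three grade 1 or grade 2 AEs of the same type", and also by three low-grade liver events. None of these rules asks for a confirmatory sample. Section 8.2.2 says that relatedness does not decide what is reported.

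What is at stake is whether the same eligibility and safety rules mean the same thing for US and international participants. An avoidable measurement step could also cost a participant, or a pause of the trial, in a very rare condition.

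**Working it through.** The plan states no figure on this point, so there is none to reproduce. The check has three parts.

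**1. Route against rule, by time point**

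| Time point | International route | US route | Rule acting on the result |
|---|---|---|---|
| Baseline (7.3.2) | Drawn locally, mailed, analysed at the study's local LabCorp | LabCorp or local facility | Platelet exclusion; reference value for grades defined against baseline |
| Day 90 (7.3.3) | Same mailed route | LabCorp or local facility | Platelet removal; grades in 8.2.1; rules in 8.5 |
| Day 210 (7.3.4) | Local draw; mailing and place of analysis not stated | Local draw; same text | Same as Day 90 |

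Mailing is explicit for two samples per international participant. One of them, Day 90, is taken after dosing has begun. Because Day 210 is open, the two period ends of the crossover could be measured by different routes in the same person.

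**2. How far a value must move to matter**

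- *Platelet exclusion or removal.* Section 7.1.1 gives a normal range of about 140,000 to 450,000. To cross 50,000, a count of 140,000 must fall by (140,000 − 50,000)/140,000 = 64%. A count of 450,000 must fall by (450,000 − 50,000)/450,000 = 89%.
- *Platelet grade 1.* This begins at the lower limit of normal, so a low-normal count needs only a small fall.
- *Potassium.* Grade 1 is any value above the upper limit of normal up to 5.5 mmol/L; grade 3 begins above 6.0 mmol/L.

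The low-grade boundaries, and so the study-wide halt, are therefore more exposed to measurement error than the platelet exclusion.

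**3. Sensitivity of the study-wide halt (illustration only)**

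Let k be the number of mailed post-baseline samples. Let p be the chance that shipping alone puts one sample into grade 1 or 2 for one given type of abnormality. Both are assumptions, and samples are treated as independent:

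P(at least 3) = 1 − Σ C(k, j) p^j (1 − p)^(k − j), summed over j = 0, 1, 2.

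For k = 6 and p = 0.20: 1 − (0.2621 + 0.3932 + 0.2458) = 0.0989.
For k = 10 and p = 0.20: 1 − (0.1074 + 0.2684 + 0.3020) = 0.3222.

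| International participants | Mailed post-baseline samples | p = 5% | p = 10% | p = 20% | p = 30% |
|---|---|---|---|---|---|
| 3 | 3 (Day 90 only) | 0.0% | 0.1% | 0.8% | 2.7% |
| 6 | 6 (Day 90 only) | 0.2% | 1.6% | 9.9% | 25.6% |
| 10 | 10 (Day 90 only) | 1.2% | 7.0% | 32.2% | 61.7% |
| 6 | 12 (if Day 210 is also mailed) | 2.0% | 11.1% | 44.2% | 74.7% |
| 10 | 20 (if Day 210 is also mailed) | 7.5% | 32.3% | 79.4% | 96.5% |

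The last two rows also assume that two results from one person count as two events. The table covers one type of abnormality and ignores genuine events, which would add to the count.

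For an individual loss, one participant out of 30 is 1/30 = 3.3% of the target in 4.1, or 1% if the figure in 10.6.1 applied.

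**The case against.** The strongest reply is that the documents contain no evidence that mailed results would be wrong. Transit time, tube type, temperature and separation are all unstated. A reader might infer that platelets will read falsely low and potassium falsely high. The documents support neither the direction nor the size of such an error, and a normal platelet count would have to drop by at least 64% to trip the exclusion. This stands: the supportable point is an uncontrolled step, not a demonstrated bias.

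Four further objections also stand, wholly or in part:

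- **Number of samples.** It is tempting to count three mailed samples per person. Only two are stated, and treating the pre-dose one as an adverse event is arguable. Section 8.1.1 ties adverse events to use of an intervention, while 8.3 records events from consent onward. On the explicit text, three low-grade results of one type after dosing must come from three different international participants.
- **Consequence.** Each event is assessed by a clinician, and the halt is temporary pending DSMB review. That softens the effect, but no repeat draw is provided for, so the assessor would have only the doubtful value.
- **Late results.** For US participants too, the blood-draw information arrives with the medication and dosing starts the day after the baseline call. Mailing can lengthen the wait, but the timing question is separate.
- **Section 13.4.1.** Its heading concerns stored research samples, so its sentence may be meant only for those. A reader might call it a flat contradiction of 7.3; it is better described as unqualified wording that needs clarifying. Likewise, NA in 7.2.4 is not a statement that nothing is shipped.

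The objection does not remove the core: shipment is prescribed in 7.3.2 and 7.3.3, the governing sections are empty, and binding rules use the results.

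**Conclusion.** The point holds as a design weakness in the laboratory route. In one subgroup, at baseline and Day 90, the platelet criteria and the laboratory-graded rules in 8.5 would act on values that have passed through an unregulated shipping step. Day 210 is unspecified.

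Its size cannot be stated. The number of international participants and the error rate are both missing from the documents. Under the assumed values the risk of an artefact-driven halt is negligible with three international participants (at most 2.7% at p = 30%, Day 90 only). It is material with six to ten participants and p of 20% or more (9.9% to 61.7%, Day 90 only). A reader might conclude that one to three mailed samples will stop the trial. They could satisfy a rule, but nothing in the documents says how likely that is.

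The primary pain endpoint is not directly affected; the exposure is in eligibility, safety data, and avoidable discontinuation or suspension. An amendment is worthwhile, but the point does not undermine the trial's main comparison.

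**What to change.** - **7.3.2 and 7.3.3:** have the CBC and metabolic panel run at the facility that draws the blood, for US and international participants alike. The dated report, with that laboratory's reference ranges, goes to the study. Delete the mail-in step, and apply the existing platelet criterion and grading table to the report.
- **7.3.4:** state the same route for Day 210, preferably with the same facility at all three time points so that grades defined against baseline compare like with like.
- **7.2.1 to 7.2.4:** replace NA with the panel, where it is analysed, and a statement that samples are not shipped to the study.
- **13.4.1:** limit the sentence on specimens to stored research samples, if that is what it means.

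The clinical thresholds are not judged here and stay unchanged.

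The cost is a short amendment. Local testing at study expense would replace international shipping and the LabCorp analysis; the documents give no prices, and section 14.4 says the study is unfunded, so the net cost is unknown. The statistical downside is several laboratories' reference ranges and units. Grades set against ULN, LLN or baseline largely absorb this, while the fixed cut-offs for potassium, platelets and haemoglobin need units checked on each report.

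If one laboratory for international samples is preferred, the alternative is to write transit limits, handling conditions and a rejection and repeat-draw rule into 7.2.3 and 7.2.4. That closes the documentation gap but leaves the cell count dependent on shipment.

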### 7.3.3 FOLLOW-UP

#### **Follow-up Phone call (Visits 2, 3, 5, 6 and 7: Days 30, 60, 120, 150 and 180 +/- 5 working days)**

- Record adverse events as reported by participant to study co-ordinator. Study coordinator will ask about gastrointestinal health, any bleeding events and unusual bruising. PI will follow up with participant to assess the adverse events and determine whether to terminate participation.
- Record participant's adherence to treatment protocol.
- Inquire about any medication and health condition changes.
- Administer HRQoL instrument.
- Self-reported will be obtained from all study subjects using the Numeric Pain Rating Scale to score the subject's pain on a 0 to 10 scale. This scale has been validated and widely used. Pain will be ascertained daily (including during the "washout" period between the two intervention periods) through a daily pain log kept by participants. The pain logs will be requested from participants at each follow-up visit and at the end of each month in the treatment periods, and data from the pain logs will be compiled and analyzed at the start and end of each of the two treatment periods (on days 0, 90, 120, and 210).
- Request participant to mail back or email their pain log and a photo of the empty bottle at end of the month
- Inform participant to start on their next 30 days aliquot of study drug.

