7.3.1 SCREENING/ENROLLMENT (VISIT 0)

- Review medical photos to confirm diagnosis of PSACH.
- Review medical history to determine eligibility based on inclusion/exclusion criteria.
- Review medications history to determine eligibility based on inclusion/exclusion criteria.
- Review urine pregnancy test to determine eligibility based on inclusion/exclusion criteria.
- Obtain written informed consent from participants which can be scanned/photographed and emailed to [contact].
- Inform participants of eligibility and enrollment into the study.
- Provide participants with specific instructions needed to participate in the study.
- Schedule phone visits for eligible participants for the duration of the study.

---

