7.3.7 SCHEDULE OF EVENTS TABLE

Visit type	Screening	Start 1 st arm	Follo w-up	Follo w-up	End 1 st arm	Wash out period	Start 2 nd arm	Follo w-up	Follo w-up	End of study	Post-study
Visit Number	0	1	2	3	4		5	6	7	8	9
Day		0	30	60	90		120	150	180	210	240

Procedures											
Check I/E criteria	X										
Obtain HIPAA clearance	X										
Informed Consent	X										
Obtain medical/medication history	X										
Urine pregnancy test	X					X					
Blood test	X					X				X	
HRQoL assessment		X	X	X	X		X	X	X	X	
Request pain logs			X	X	X		X	X	X	X	
Pain assessment (compile and analyze pain monthly average from pain logs)		X			X		X			X	
Request unused medication or photo of empty bottle			X	X	X			X	X	X	
SE/AE/SAE ascertainment			X	X	X		X	X	X	X	X
Query change in medications		X	X	X	X		X	X	X	X	
Query change in health status		X	X	X	X		X	X	X	X	
Blinding success evaluation					x					x	
Asked to start next month's dose		X	X	X			X	X	X		
Asked to stop taking all study drugs					X					X	

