Alkaline phosphatase increased	>ULN-2.5x ULN if baseline was normal; 2.0 - 2.5 x baseline if baseline was abnormal	>2.5-5.0x ULN if baseline was normal; >2.5 - 5.0 x baseline if baseline was abnormal	>5.0-20.0x ULN if baseline was normal; >5.0 - 20.0 x baseline if baseline was abnormal	>20.0x ULN if baseline was normal; >20.0 x baseline if baseline was abnormal	-
Aspartate aminotransferase increased	>ULN-3.0x ULN if baseline was normal; 1.5 - 3.0 x	>3.0-5.0x ULN if baseline was normal; >3.0 - 5.0 x baseline if	>5.0-20.0x ULN if baseline was normal; >5.0 - 20.0 x baseline if	>20.0x ULN if baseline was normal; >20.0 x baseline if	-

	baseline if baseline was abnormal	baseline was abnormal	baseline was abnormal	baseline was abnormal	
Blood bilirubin increased	>ULN-1.5x ULN if baseline was normal; > 1.0 - 1.5 x baseline if baseline was abnormal	>1.5-3.0x ULN if baseline was normal; >1.5 - 3.0 x baseline if baseline was abnormal	>3.0-10.0x ULN if baseline was normal; >3.0 - 10.0 x baseline if baseline was abnormal	>10.0x ULN if baseline was normal; >10.0 x baseline if baseline was abnormal	-
Gastrointestinal Disorders					
Nausea	Loss of appetite without alteration in eating habits	Oral intake decreased without significant weight loss, dehydration or malnutrition	Inadequate oral caloric or fluid intake; tube feeding, TPN, or hospitalization indicated	-	-
Diarrhea	Increase of <4 stools per day over baseline; mild increase in ostomy output compared to baseline	Increase of 4 - 6 stools per day over baseline; moderate increase in ostomy output compared to baseline; limiting instrumental ADL	Increase of >=7 stools per day over baseline; hospitalization indicated; severe increase in ostomy output compared to baseline; limiting self care ADL	Life-threatening consequences; urgent intervention indicated	Death
Platelet count decreased	<LLN- 75,000/mm  ; <LLN -75.0 x 10  /L	<75,000 - 50,000/mm  ; <75.0- 50.0 x 10  /L	<50,000 - 25,000/mm  ; <50.0- 25.0 x 10  /L	<25,000/mm  ; <25.0 x 10  /L	-
Anemia	Hemoglobin (Hgb) <LLN - 10.0 g/dL; <LLN - 6.2 mmol/L; <LLN - 100 g/L	Hgb <10.0 - 8.0 g/dL; <6.2 -4.9 mmol/L; <100 - 80g/L	Hgb <8.0 g/dL; <4.9 mmol/L; <80 g/L; transfusion indicated	Life-threatening consequences; urgent intervention indicated	Death

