## 8.3 TIME PERIOD AND FREQUENCY FOR EVENT ASSESSMENT AND FOLLOW-UP

The occurrence of an AE or SAE may come to the attention of study personnel during study phone interviews with the study participants or upon review by the DSMB. All AEs including local and systemic reactions not meeting the criteria for SAEs will be captured on the appropriate case report forms. Information to be collected includes event description, time of onset, clinician's assessment of severity, relationship to study drug (assessed only by those with the training and authority to make a diagnosis), and time of resolution/stabilization of the event. All AEs occurring while on study will be documented appropriately in the database regardless of relationship. All AEs will be followed to adequate resolution.

Any PSACH-related medical issue present at the time the participant is screened will be considered as baseline and not reported as an AE. However, if the study participant's condition deteriorates at any time during the study, it will be recorded as an AE. Unanticipated problems will be recorded in the data collection system throughout the study. Changes in the severity of an AE will be documented to allow an assessment of the duration of the event at each level of severity to be performed. AEs characterized as intermittent require documentation of onset and duration of each episode.

The study staff will record all reportable events with start dates occurring any time after informed consent is obtained until 7 (for non-serious AEs) or 30 days (for SAEs) after the last day of study participation. At each study visit, the study staff will inquire about the occurrence of AE/SAEs since the last visit. Events will be followed for outcome information until resolution or stabilization.

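### No gastrointestinal, bleeding or bruising questions and no usual stool frequency are recorded before the first dose in period 1, so early diarrhea grades rest on recall

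*Combined protocol and SAP*

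**What the plan says.** Section 7.3.3 (Visits 2, 3, 5, 6, 7 and, separately, Visit 4) and section 7.3.4 (Visit 8) carry the same instruction: "Study coordinator will ask about gastrointestinal health, any bleeding events and unusual bruising".

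The lists for the visits before dosing do not carry it. At Visit 0 the health content is "Review medical history to determine eligibility based on inclusion/exclusion criteria". At Visit 1 (Day 0) it is "Query participants about any changes in inclusion/exclusion criteria", together with the blood draw and the quality-of-life instrument. After that call, "Patients will be asked to start taking study medication on the next day".

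In the schedule table (7.3.7) the row "SE/AE/SAE ascertainment" is blank at Visits 0 and 1 and first ticked at Visit 2. The row for change in health status is ticked at Visit 1. Section 8.3 says: "At each study visit, the study staff will inquire about the occurrence of AE/SAEs since the last visit".

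The grading table in 8.2.1 defines grade 1 diarrhea as "Increase of <4 stools per day over baseline; mild increase in ostomy output compared to baseline". Grades 2 and 3 also refer to an increase over baseline. Section 2.3.1 lists nausea and diarrhea as the expected adverse events.

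**The concern.** A grade defined as a change needs a starting value. For the liver enzymes, where the grading table also refers to baseline, the schedule provides a blood test at screening. For bowel habit, bleeding and bruising nothing comparable is collected before the first dose. A participant who has always had loose stools or who bruises easily is first asked about it when already on product.

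Three features of the plan make that matter:

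- Under 8.2.2 a temporal relationship with the study agent is enough for an event to be classed as related.
- Section 10.4.4 tabulates crude rates of study-related events with one-sided 95% intervals. It names no comparison with placebo that would absorb background complaints.
- The study-wide count in 8.5 of three grade 1 or 2 events of the same type requires neither relatedness nor onset after the first dose. The individual counts in 8.5 also include grade 1 and grade 2 events.

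The gap falls on the events that the protocol itself expects.

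**Working it through.** The plan states no figure on this point, so there is none to reproduce. The check sets the visit lists, the schedule, the grading table and the recording rules side by side.

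**1. Where the questions are asked (7.3.1 to 7.3.4 and 7.3.7)**

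| Visit | Day | Targeted questions in the text | Adverse event row in the schedule |
|---|---|---|---|
| 0 | screening | no | blank |
| 1 | 0 | no | blank |
| 2, 3 | 30, 60 | yes | ticked |
| 4 | 90 | yes | ticked |
| 5 | 120 (start of second arm) | yes | ticked |
| 6, 7 | 150, 180 | yes | ticked |
| 8 | 210 | yes | ticked |
| 9 | 240 | general query only | ticked |

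The blank at Visit 0 is harmless, because consent is obtained there and the recording window opens with consent. The blank at Visit 1 disagrees with 8.3, which calls for an inquiry at every study visit.

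**2. Time on product before the first targeted question**

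The first dose is on Day 1 and Visit 2 is on Day 30: 30 − 1 = 29 days. The window of 5 working days is about 7 calendar days, so Visit 2 can fall between Day 23 and Day 37, which is 22 to 36 days on product. The product is placebo or resveratrol, depending on sequence.

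**3. What the diarrhea grade needs**

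In stools per day over baseline, grade 1 is an increase below 4, grade 2 is 4 to 6, and grade 3 is 7 or more. No visit in 7.3 records usual stools per day. An increase of 3 is grade 1 and an increase of 4 is grade 2, so an error of one stool per day in the recalled baseline can move the grade.

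**4. Scale of the exposure in 8.5, under assumption**

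The documents give no prevalence of mild bowel or bruising complaints in this population. Assume a prevalence p of one type of complaint, independent between participants, and suppose every such complaint were counted as an adverse event. The chance that background alone reaches three is then

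P(X ≥ 3) = 1 − Σ (k = 0 to 2) C(n, k) p^k (1 − p)^(n − k).

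For n = 30 and p = 0.05: 1 − (0.2146 + 0.3389 + 0.2586) = 0.188.

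| Assumed p | Expected count, n = 30 | P(X ≥ 3), n = 30 | P(X ≥ 3), n = 100 |
|---|---|---|---|
| 2% | 0.6 | 0.022 | 0.323 |
| 5% | 1.5 | 0.188 | 0.882 |
| 10% | 3.0 | 0.589 | 0.998 |
| 20% | 6.0 | 0.956 | above 0.999 |

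The size of 30 is from 4.1 and 10.5. The column for 100 is shown because 10.6.1 gives that number. These are ceilings: section 8.3 excludes any complaint correctly dated to before consent. The 33% placebo rate of nausea and diarrhea in 2.3.1 is not used as p. It comes from a 52-week dementia trial, and the protocol attributes the high background there to a concomitant medicine.

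**The case against.** The strongest reply is that 8.3 already governs this. It records only events that start after consent, asks for time of onset, tracks changes in severity and documents each episode of an intermittent event. A long-standing complaint is therefore not reportable. A usual bowel habit that has not changed is no increase and earns no grade. A medical history is taken by interview (7.1.1), and a change in health status is asked about at Visit 1. Eligibility requires good health apart from PSACH complications and excludes other conditions, NSAIDs, aspirin and blood thinners. In period 2 the Day 120 call asks the targeted questions at the start of the second arm, after the washout. Reaching the count in 8.5 leads to a temporary halt with review by the DSMB.

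Most of this stands, and it limits the point. A reader might infer that complaints present before dosing will be counted as on-product events. The documents do not support that, because the rule on start dates excludes those that began before consent. A reader might also infer that diarrhea cannot be graded. It can be, from recall.

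Some of the concern survives. Onset and usual frequency in period 1 are reconstructed about a month later with no earlier record to check against. The medical history serves diagnosis and eligibility, and the Visit 1 queries ask about change, so none of them is directed at bowel habit or bruising. The baseline rule in 8.3 names only PSACH-related issues. Events that start between consent and the first dose are reportable, and 8.5 does not set them apart. The Day 120 call does not specify stool frequency either.

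**Conclusion.** The point holds as a gap in baseline data collection. In period 1 the targeted questions first come after about 29 days on product (22 to 36 with the visit window). Diarrhea grades 1 to 3 there depend on a recalled baseline, and complaints that predate dosing can be misdated and enter the rates in 10.4.4 and the counts in 8.5. The blank adverse event cell at Visit 1 is a plain inconsistency with 8.3.

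The size of the effect is unknown. The range of 0.022 to 0.956 at n = 30 rests on assumed prevalences of 2% to 20%, with every background complaint counted. It should not be read as the likelihood of a halt.

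A reader might also infer that the gap biases resveratrol against placebo. That is not supported: the questions start at the same visit in both sequences, so no direction of bias is shown. The exposure lies in the crude rates, the pooled count and the individual counts.

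**What to change.** - In 7.3.2, add the same gastrointestinal, bleeding and bruising questions to the Visit 1 (Day 0) call, plus usual stools per day. In 7.3.3, ask usual stools per day at Visit 5 as well.
- In 7.3.7, tick the adverse event row at Visit 1, to agree with 8.3.
- In 8.2.1, state that these answers are the recorded baseline for the symptom grades that refer to baseline.
- Have the sponsor reconcile 8.3 and 8.5 on how non-PSACH complaints present before dosing are treated.

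Leave the definition of an event and the counts in 8.5 as they are. Redefining an on-product event as a new complaint or a rise in grade over Visit 1 would change what feeds the halting and discontinuation counts. It would also conflict with 8.3, which documents each episode of an intermittent event and records events from consent onward.

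The cost is a slightly longer Visit 1 call, one extra question at Visit 5, one tick in the table and a few sentences of text. It is worth doing before enrollment, because a baseline missed before the first dose cannot be recovered afterward except by recall.
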